## 5 INTRODUCTION

DNA-dependent protein kinase (DNA-PK) plays an important role in cellular survival after DNA damage via its activity repairing rare but lethal double strand breaks (DSBs) by non-homologous end joining (NHEJ), as the catalytic subunit of a complex of proteins. This activity is crucial because the DSBs rapidly lead to cell death if not quickly and efficiently repaired. Targeting DNA-PK provides a striking opportunity to improve cancer patient outcomes because the majority of cancer patients will receive therapies whose sole objective is to induce DSBs in tumor cells. These therapies include radiation therapy (RT) and certain chemotherapies such as the topoisomerase II inhibitors etoposide and anthracylines such as pegylated liposomal doxorubicin (PLD). While these therapies have achieved some success clinically, ultimately many of these treatments fail due to insufficient local control, local recurrence, and disseminated disease. It is therefore critical to develop new therapeutic strategies to improve loco-regional control as well to impact disseminated disease.

VX-984 (EMD Serono internal compound code: M9831) is a novel potent and selective inhibitor of DNA-PK (median inhibition constant [Ki] = 2 nM) with minimal activity against related and unrelated kinases. This includes 4 highly-related phosphatidylinositol-3-kinase (PI3K) isoforms as well as the other class members ataxia telangiectasia mutated kinase (ATM), ataxia telangiectasia muted and Rad3-related kinase (ATR), and mammalian target of rapamycin (mTor). VX-984 inhibits DNA-PK function in cells with a concentration associated with 50% inhibition [IC50] of 88 nM and sensitizes most cancer cell lines and primary patient derived tumor cells to the lethal effects of RT and to chemotherapies that cause DSBs in DNA. Importantly, additivity to strong synergy is also observed with some DSB-inducing agents such as doxorubicin.

VX-984 is deuterated, which offers the possibility to decrease metabolism by aldehyde

oxidase to increase stability in human hepatocytes and, thereby, potentially substantially lowering the required efficacious dose.

In patient-derived xenograft models using ovarian cancer and in multiple cancer cell line models, VX-984 in combination with PLD significantly enhanced the anticancer activity of

PLD when VX-984 was administered 16 hours after PLD, and was generally well-tolerated. VX-984 showed no single-agent efficacy in the tumor models evaluated.

Based on the nonclinical observations, VX-984 had the potential to have a substantial therapeutic impact on malignancies with high unmet need and in which DSB inducers such as PLD is used as standard of care (SOC), such as recurrent or metastatic endometrial cancer.

Endometrial cancer accounts for the 90% of uterine cancers. There are approximately 50,000 newly diagnosed patients in the US and 44,000 in the 5 most populous EU countries (EU5) expected in 2015. Less than a quarter of endometrial cancer presents in an advanced stage, where it is generally treated with platinum-based chemotherapy alone or following surgery. Approximately 60% of these patients ultimately go on to receive subsequent treatment, representing approximately 3,800 patients in the US and 3,100 patients in the EU5 annually. Treatment guidelines recommend single-agent chemotherapy in the second-line setting, though there is no currently approved treatment.

Study VX15-984-001 (Study 001) is an open-label, first-in-human (FIH) study comprised of 2 parts (Part A and Part B). The purpose of Part A is to determine the maximum tolerated dose (MTD) and to characterize the safety, tolerability, and pharmacokinetic (PK) profile of VX-984 administered orally in multiple doses after PLD in adult patients with advanced solid tumors who have progressed through standard therapeutic options and for whom no standard therapy is available or PLD may be considered SOC. After the MTD of VX-984 in combination with PLD has been determined, Part B will evaluate the anti-tumor potential and safety of VX-984 in combination with PLD in subjects with recurrent or metastatic endometrial cancer who have progressed on a prior platinum regimen.

This study will support the development of VX-984 in combination with DNA DSB-inducing agents by providing preliminary safety and efficacy data to guide subsequent development.

## 6 STUDY OBJECTIVES

## 6.1 Part A

## 6.1.1 Primary Objectives

- To evaluate the safety and tolerability of VX-984 administered alone and in combination with PLD in subjects with advanced solid tumors
- To determine the maximum tolerated dose (MTD) of VX-984 in combination with PLD in subjects with advanced solid tumors.

## 6.1.2 Secondary Objectives

- To evaluate the pharmacokinetics (PK) of VX-984 when administered alone and in combination with PLD in subjects with advanced solid tumors
- To evaluate the PK of PLD when administered in combination with VX-984 in subjects with advanced solid tumors
- To evaluate preliminary anti-tumor activity of VX-984 in combination with PLD in subjects with advanced solid tumors.

# 6.1.3 Exploratory Objectives

- To assess tumor response by tumor volume and tumor necrosis in subjects administered VX-984 in combination with PLD
- To assess correlations between prior treatment response and treatment outcome.

## 6.2 Part B

# 6.2.1 Primary Objectives

- To evaluate the safety and tolerability of VX-984 administered in combination with PLD in subjects with recurrent or metastatic endometrial cancer who have progressed on a prior platinum regimen
- To assess the overall response to VX-984 administered in combination with PLD in subjects with recurrent or metastatic endometrial cancer who have progressed on a prior platinum regimen.

## 6.2.2 Secondary Objectives

- To assess progression free survival (PFS) in subjects with recurrent or metastatic endometrial cancer who have progressed on a prior platinum regimen administered VX-984 in combination with PLD
- To assess response duration (RD) in subjects with recurrent or metastatic endometrial cancer who have progressed on a prior platinum regimen administered VX-984 in combination with PLD
- To assess overall survival (OS) in subjects with recurrent or metastatic endometrial cancer who have progressed on a prior platinum regimen administered VX-984 in combination with PLD
- To assess clinical benefit in subjects with recurrent or metastatic endometrial cancer who
  have progressed on a prior platinum regimen administered VX-984 in combination with
  PLD as measured by complete response (CR), partial response (PR), or stable disease
  (SD) of 4 months or greater
- To evaluate the PK of VX-984 when administered in combination with PLD in subjects with recurrent or metastatic endometrial cancer who have progressed on a prior platinum regimen.

# 6.2.3 Exploratory Objectives

• CCI

- To assess tumor response by tumor volume and tumor necrosis in subjects with previously-treated endometrial cancer, administered VX-984 in combination with PLD
- To assess correlations between prior treatment response and treatment outcome

## 7 STUDY ENDPOINTS

## 7.1 Part A

## 7.1.1 Primary Endpoints

- Safety parameters, including adverse events (AEs), dose-limiting toxicities (DLTs), clinical laboratory values (serum chemistry and hematology), vital signs, echocardiograms, and electrocardiogram (ECG) assessments
- MTD of VX-984 in combination with PLD.

# 7.1.2 Secondary Endpoints

- Plasma PK parameter estimates of VX-984, administered alone and in combination with PLD, derived from plasma concentration-time data
- Plasma PK parameter estimates of PLD administered in combination with VX-984, derived from plasma concentration-time data
- Preliminary evidence of anti-tumor activity, including tumor response as evaluated by Response Criteria Evaluation RECIST 1.1 and tumor markers.

# 7.1.3 Exploratory Endpoints

- CCI
- Tumor response as assessed by tumor volume and tumor necrosis using 3D computed tomography (CT) scans
- Tumor response as assessed by historical and on-treatment tumor growth dynamics
- CCI

## 7.2 Part B

# 7.2.1 Primary Endpoints

- Safety parameters, including AEs, clinical laboratory values (serum chemistry and hematology), vital signs, and ECG assessments
- Objective response rate (ORR) as evaluated by CT scan per RECIST 1.1.

## 7.2.2 Secondary Endpoints

- PFS
- RD as evaluated by CT scan and quantified by RECIST 1.1
- OS
- Clinical benefit (CR + PR + SD of at least 4 months)
- Plasma PK parameter estimates of VX-984 when administered in combination with PLD, derived from plasma concentration-time data.

# 7.2.3 Exploratory Endpoints

- · CCI
- Tumor response as assessed by tumor volume and tumor necrosis using 3D CT scans
- Tumor response as assessed by historical and on-treatment tumor growth dynamics
- CCI

## 8 STUDY DESIGN

## 8.1 Overview of Study Design

This is an open-label, multicenter, single-arm, FIH, dose-escalation study in subjects with solid tumors who have progressed through standard therapeutic options and for whom no standard therapy is available or PLD may be considered SOC (Part A) followed by an expansion phase in subjects with recurrent or metastatic endometrial cancer who have progressed on a prior platinum regimen (Part B).

Part A will be a dose escalation study to evaluate the safety, tolerability, and PK of VX-984 when administered in combination with PLD. At each VX-984 dose level tested, subjects will receive VX-984 once daily (qd) alone on Days -14 to -12 of a 14-day Lead-in Period before receiving combination treatment with PLD. Following the single agent Lead-in Period, subjects will receive PLD on Day 1 and VX-984 qd on Days 2 to 4 of a 28-day cycle. The Lead-in Period will be required only if the dose of VX-984 is escalated beyond the highest dose of VX-984 previously tolerated in a Lead-in Period. This part will establish the MTD of VX-984 in combination with PLD (Figure 8-1).

Part B will be an expanded cohort study to confirm the safety, tolerability, PK, and potential anti-tumor activity of VX-984 in combination with PLD at the MTD or lower, as determined during Part A (Figure 8-1).

[figure not shown]

Figure 8-1 Overview of Study Design

- a. The Lead-in Period will be required only if the dose of VX-984 exceeds a dose previously tolerated in a Lead-in Period.
- b. Subjects in Part A will receive up to 6 cycles of treatment. Subjects with tumors responding to treatment may continue on treatment past 6 cycles with the agreement of the Investigator and medical monitor.
- Subjects in Part B will receive treatment until disease progression, unacceptable toxicity, or withdrawal of consent.
- d. Follow-up will include a Safety Follow-up Visit 28 (± 7) days after the last dose of study drug and a radiologic follow-up visit 5 (± 1) weeks after the last cycle of chemotherapy, and survival follow-up assessment at the last subject last visit. In Part B, for subjects without disease progression, long-term follow-up, including, as indicated, staging CT scans and/or follow-up communications, may continue for up to 1 year.

# 8.1.1 Screening (Parts A and B)

Screening Visit assessments are listed in Table 3-1.

Screening will occur within 14 days before administration of study drug. The Investigator (or an appropriate authorized designee at the study site) will obtain informed consent from each subject. If the time between screening and dosing exceeds 14 days as a result of unexpected operational delays (e.g., delayed drug shipment), then subjects do not require re-screening if laboratory results within 7 days of the first dose of study drug meet the eligibility criteria. Subjects who are unable to dose within the screening window because of substantial complications or disease progression will be replaced.

To prepare for study participation, subjects will be instructed on the study restrictions (Section 9.3).

A subject who qualified but did not enroll for an earlier cohort may be enrolled in a subsequent cohort with no required re-screening if predose laboratory results and World

Health Organization (WHO) performance status meet the eligibility criteria. Baseline CT scan will need to be repeated if more than 28 days have passed since most recent CT scan.

Subjects who do not meet the eligibility criteria may not be rescreened, with the following exceptions:

- Subjects who receive red blood cell transfusion or fluid replacement therapy
- In the Investigator's opinion, the reason for initial screen failure is due to a clearly temporary condition (e.g., incomplete recovery from recent surgery; inadequate time frame since prior chemotherapy)
- Subjects who met all eligibility criteria but are not able to obtain required documentation within the allotted screening window
- Subjects who met all eligibility criteria but transiently (for personal reasons) are unable to commit to all study procedures
- Subjects who were screened under a prior version of the protocol and did not meet any exclusion criterion, with the exception of a criterion that was updated in a subsequent version of the protocol.

The medical monitor must authorize re-testing in all cases except when subjects need to receive red blood cell transfusion or fluid replacement therapy. In this case, medical monitor approval is not required for re-testing. Any subject granted approval by the medical monitor for the exceptions listed above may have the screening window extended by 1 week before needing to undergo any rescreening assessments. If more than 35 days have elapsed from screening before first dose of study drug, all screening assessments need to be repeated. Repetition of any screening assessment that did not meet eligibility criteria is not permitted, unless there is clear evidence of a laboratory error (e.g., hemolysis of sample).

## 8.1.2 Treatment Period

## 8.1.2.1 Part A

Treatment Period assessments are listed in Table 3-2 for the single agent Lead-in Period and in Table 3-3 for the combination treatment of VX-984 with PLD in Part A.

## 8.1.2.1.1 Starting Dose and Dosing Schedule

The starting dose of VX-984 will be 120 mg qd and PLD will be 40 mg/m^2. The rationale for selection of the starting dose and dosing schedule for VX-984 and PLD is provided in Section 8.2.2.

For each VX-984 dose level tested, subjects will receive VX-984 qd alone on Days -14 to -12 of a 14-day Lead-in Period. Following the single agent Lead-in Period, subjects will receive PLD on Day 1 and VX-984 qd on Days 2 to 4 of a 28-day cycle. The Lead-in Period will be required only if the dose of VX-984 is escalated beyond the highest dose of VX-984 previously tolerated in a Lead-in Period.

Criteria for study drug administration on Day 1 of Cycle 1 and subsequent cycles are summarized in Section 10.2.

## 8.1.2.1.2 Guidelines for Dose Escalation

Three subjects will be enrolled at the starting dose of VX-984 and PLD. If the starting dose of VX-984 is tolerated alone in the 14-day Lead-in Period and in combination with PLD through 1 cycle (28 days) without a DLT or Common Terminology Criteria for Adverse Events (CTCAE) Grade 3 or worse toxicities in any of these 3 subjects and without a CTCAE Grade 2 toxicity in 2 subjects, the dose of VX-984 may be increased by up to 100% in a subsequent cohort of 3 subjects while holding the dose of PLD constant. Safety data, including AEs, laboratory values, and ECG results, obtained through the end of Cycle 1, as well as available PK data, will be assessed to determine the dose of VX-984 that will be used for the next cohort.

In this way, the dose of VX-984 will be escalated with 40 mg/m^2 of PLD in subsequent cohorts of 3 subjects until:

- 1 subject has a treatment-related or possibly-related DLT or toxicity of CTCAE Grade 3 or worse; or
- 2 subjects (who may be in different cohorts) have a toxicity of CTCAE Grade 2.

Subsequent dose escalation will proceed depending on the toxicity as described:

- In the event of a treatment-related or possibly-related toxicity of CTCAE Grade 3 or worse toxicity in 1 subject (that is not considered a DLT), or treatment-related or possibly-related toxicity of CTCAE Grade 2 in 2 subjects (who may be in different cohorts), the dose escalation will continue with a more conservative dose escalation (up to 50%). The dose of VX-984 will continue to be escalated with 40 mg/m² of PLD in subsequent cohorts of 3 subjects until there is a DLT through the end of Cycle 1
- In the event of a DLT, an adaptive Bayesian logistic regression model (BLRM) will be used to determine the dose for the subsequent cohorts or determine if the current dose level should be expanded. The adaptive BLRM will be guided by the escalation overdose control (EWOC) principle to control the risk of DLT in future subjects as described in Section 12.3.3.2. At each predicted dose, 3 to 6 subjects will be enrolled in each cohort at the discretion of the sponsor and Investigators as described in Section 8.1.2.1.8. If more than 3 subjects are enrolled, the first 3 subjects will receive VX-984 in the Lead-in Period and if no DLT is observed with VX-984 dosing then the additional subjects in the cohort will not have the Lead-in Period. The Lead-in Period will be required only if the dose of VX-984 is escalated beyond the highest dose of VX-984 previously tolerated in a Lead-in Period
- If 2 subjects in a previously untested dose level experience a DLT, enrollment to that cohort will stop, the BLRM will be updated and the next cohort will be opened at a lower dose level or an intermediate dose level that satisfies the EWOC criteria. However, if 2 subjects in a new cohort at a previously tested dose level experience a DLT (e.g., a total of 8 subjects are tested on this dose level with 2 DLTs observed), further enrollment to that cohort will stop, the BLRM will be updated with this new information and re-evaluation of the available safety, PK and PD data will occur. By

incorporating information gained at the preceding dose levels, additional subjects may be enrolled into the current dose level only if the dose still meets the EWOC criteria and as agreed by the sponsor and Investigators.

A subject will be considered as evaluable for dose determination if they have a DLT during Cycle 1 or the preceding Lead-in Period, or meet the minimum treatment and safety evaluation requirements for the first cycle as outlined in Subject Evaluability.

After completion of Cycle 1 of each cohort (3 to 6 subjects), available safety, PK, and efficacy information as well as recommendations from the Bayesian model will be used to determine the dose for the next cohort, with the following 2 exceptions:

- 1. For cohorts requiring 3 or more evaluable subjects, if only 2 evaluable subjects are available for assessment (all others drop out), and neither subject has had a treatment-related or possibly-related toxicity greater than CTCAE Grade 1, then 2 subjects will be considered sufficient for decision-making
- 2. If the first 2 subjects in a cohort have a DLT, further enrollment to the study will be temporarily suspended and the Bayesian model will be updated with this new information. If the Bayesian model supports enrolling the next cohort at the dose level where 2 DLTs occurred, or at a higher dose level, the relevant data and rationale will be discussed and agreed upon by sponsor and the Investigators of the escalation phase. If sponsor and the Investigators agree that it is medically appropriate to enroll an additional cohort at the dose level where 2 DLTs occurred or at a higher dose, the data and rationale supporting this decision will be documented.

Following the principle of escalation with overdose control (EWOC), after each cohort the recommended dose will be the one with the highest posterior probability of the DLT rate falling in the target toxicity interval [0.166, 0.333) among the doses fulfilling EWOC. Per EWOC, it should be unlikely (< 25% posterior probability) that the DLT rate at the dose will exceed 0.333.

For further understanding of the safety, tolerability, and PK of VX 984 in combination with PLD, additional cohorts of subjects may be enrolled at preceding dose levels, or to intermediate dose levels before or while proceeding with further dose escalation. The maximum planned dose of VX-984 is 2000 mg during escalation, however, higher doses up to 3000 mg may be allowed depending on the observed safety, PK, and PD, and based on recommendation of the BLRM.

After repeating the above steps, the dose escalation of VX-984 will continue with a constant dose of PLD at 40 mg/m^2 until MTD is achieved.

If a dose of VX-984 is not tolerated with PLD at 40 mg/m², then the VX-984 dose may be reduced by up to 50% with a constant dose of PLD at 40 mg/m² or the dose of PLD will be reduced by 25% (30 mg/m²) or lower with a constant dose of VX-984. These doses will be explored in subsequent cohorts at the discretion of the Investigators and sponsor. If daily dosing of VX-984 for 3 days after PLD is not tolerated during initial dose escalation, less frequent dosing of VX-984 may be explored in subsequent cohorts.

Details on dose modifications for drug-related toxicity are provided in Section 10.5.

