- If 2 subjects in a previously untested dose level experience a DLT, enrollment to that cohort will stop, the BLRM will be updated and the next cohort will be opened at a lower dose level or an intermediate dose level that satisfies the escalation overdose control (EWOC) criteria. However, if 2 subjects in a new cohort at a previously tested dose level experience a DLT (e.g., a total of 8 subjects are tested on this dose level with 2 DLTs observed), further enrollment to that cohort will stop, the

BLRM will be updated with this new information and re-evaluation of the available safety, PK and PD data will occur. By incorporating information gained at the preceding dose levels, additional subjects may be enrolled into the current dose level only if the dose still meets the EWOC criteria and as agreed by the sponsor and Investigators.

Subjects will be considered as evaluable for dose determination if they have a DLT during Cycle 1 or the preceding Lead-in Period or meet the minimum treatment and safety evaluation requirements for the first cycle as outline in the protocol.

After completion of Cycle 1 of each cohort (3 to 6 subjects), available safety, PK, and efficacy information as well as recommendations from the Bayesian model will be used to determine the dose for the next cohort. The adaptive BLRM will be guided by the EWOC principle to control the risk of DLT in future subjects (see Statistical Analysis section for details).

After repeating the above steps, the dose escalation of VX-984 will continue with a constant dose of PLD at 40 mg/m² until MTD of VX-984 with PLD at 40 mg/m² is achieved. The maximum planned dose of VX-984 is 2000 mg; however, higher doses up to 3000 mg may be allowed depending on the observed safety, PK, and PD, and based on recommendation of the BLRM.

If a dose of VX-984 is not tolerated with PLD at 40 mg/m², then the VX-984 dose will be reduced by up to 50% with a constant dose of PLD at 40 mg/m² or the dose of PLD will be reduced by 25% (30 mg/m²) or lower with a constant dose of VX-984. These doses will be explored in subsequent cohorts at the discretion of the Investigators and sponsor until the MTD is established with PLD at 30 mg/m² or lower. If daily dosing of VX-984 for 3 days after PLD is not tolerated during initial dose escalation, less frequent dosing of VX-984 may be explored in subsequent cohorts.

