# **Exploratory Assessments**

#### **Statistical Analyses**

#### **Bayesian Adaptive Model:**

The adaptive BLRM with EWOC principle will be used, with the following 2 exceptions:

- 1. For cohorts requiring 3 or more evaluable subjects, if only 2 evaluable subjects are available for assessment (all others drop out), and neither subject has had a treatment-related or possibly-related toxicity greater than CTCAE Grade 1, then 2 subjects will be considered sufficient for decision-making
- 2. If the first 2 subjects in a cohort have DLTs, no additional subjects will be enrolled into that cohort until the Bayesian model has been updated with this new information. Likewise, the model will be re-evaluated if 2 subjects in a cohort have DLTs before the enrollment of any additional subjects.

Model:

$$logit\{\pi(d_j, x_1, ..., x_k)\} = \log(\alpha) + \beta \log\left(\frac{d_j}{d^*}\right) + \sum_{i=1}^k \gamma_i x_i$$

 Under-dosing:
  $\pi(d) \in [0.00, 0.166)$  

 Target toxicity:
  $\pi(d) \in [0.166, 0.333)$  

 Excessive toxicity:
  $\pi(d) \in [0.333, 1.00]$ 

The recommended dose for the next cohort will fulfill the following 2 criteria:

- 1. Dose that maximizes probability that true DLT rate is in the target toxicity interval [0.166, 0.333)
- 2. With overdose control: less than 25% probability of the true DLT rate in the excessive toxicity interval [0.333, 1].

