## 8.1.2.1.8 Dose Escalation Process/Decision Making

At the end of each treatment cohort, the sponsor will convene a teleconference with the Investigators of the escalation phase. At the dose escalation teleconference, the clinical course (safety information including both DLTs and all CTCAE Grade ≥ 2 toxicity data during Cycle 1 as well as PK data) for each subject in the current dose cohort will be discussed. Updated safety data on other ongoing subjects, including data in later cycles, will be discussed as well.

Safety laboratory results and AEs occurring up to and including Day 28 of Cycle 1 will be reviewed as soon as they are available for a given cohort. Assessments for Day 28 of Cycle 1 must take place before dosing on Day 1 of Cycle 2. In this case, predose assessments on Day 1 of Cycle 2 will be used for DLT evaluation. DLTs that may have occurred through Day 28 of Cycle 1 of the current cohort, as well as DLTs that have occurred in prior cohorts in later cycles, will be identified.

To determine the dose regimen for the next cohort, the available toxicity information (including DLTs, AEs that are not DLTs, and AE information post-Cycle 1), PK, PD, and anti-tumor activity information, as well as the recommendations from the BLRM will be evaluated by the Investigators and sponsor study personnel (including the sponsor physician and statistician responsible for this study) at the dose decision meeting. The parties must reach a consensus on whether to declare MTD, escalate the dose any further, or whether to de-escalate and/or expand recruitment into particular cohorts.

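### When the first two subjects at an untested dose both have DLTs, the protocol gives two different rules for the next dose and does not say which governs

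*Protocol*

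**What the plan says.** Protocol 8.1.2.1.2 and the matching synopsis text set a two-DLT rule that depends on whether the dose level has been tested before. For an untested level: "If 2 subjects in a previously untested dose level experience a DLT, enrollment to that cohort will stop". The consequence is that "the BLRM will be updated and the next cohort will be opened at a lower dose level or an intermediate dose level" meeting the overdose (EWOC) criterion. For a previously tested level, a separate branch allows more subjects at the current dose if EWOC is still met and the sponsor and Investigators agree.

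The same section then gives two exceptions to the general sentence on choosing the next dose after Cycle 1. Exception 2 begins: "If the first 2 subjects in a cohort have a DLT, further enrollment to the study will be temporarily suspended". It goes on: "If the Bayesian model supports enrolling the next cohort at the dose level where 2 DLTs occurred, or at a higher dose level", the sponsor and Investigators discuss the data and, if they agree, document their rationale.

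The synopsis (Bayesian Adaptive Model) and Section 12.3.3.2 restate exception 2 as a pause and model update only: "If the first 2 subjects in a cohort have DLTs, no additional subjects will be enrolled into that cohort until the Bayesian model" is updated. Neither mentions the same or a higher dose.

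**The concern.** The trigger of exception 2 is the first two subjects in a cohort, with no limit to tested levels. Two DLTs in the first two subjects at a new level therefore satisfy both rules. One prescribes a lower or intermediate dose; the other leaves the same or a higher dose open.

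If exception 2 is taken as the more specific rule, the ordering is perverse. Two DLTs in the first two subjects (100%) could be followed by the same or a higher dose. Two DLTs among three to six subjects at the same untested level (67% down to 33%) must be followed by a lower or intermediate one. The stronger signal would get the looser rule.

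What is at stake is one clear instruction, in a first-in-human escalation, on whether a dose may be repeated or exceeded after its first two subjects both had DLTs.

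**Working it through.** **1. The texts side by side**

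| | Two-DLT rule (8.1.2.1.2, synopsis) | Exception 2 (8.1.2.1.2) | Exception 2 (synopsis model section, 12.3.3.2) |
|---|---|---|---|
| Trigger | 2 DLTs at an untested level | First 2 subjects in any cohort have a DLT | First 2 subjects in any cohort have DLTs |
| Next dose | Lower or intermediate, meeting EWOC | Same or higher possible if the model supports it and the parties agree | Not stated; pause and model update only |

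Exception 2 is attached to the general next-dose sentence, not to the two-DLT bullet. No sentence sets an order of precedence. SAP 15.1 defines the MTD and tabulates DLTs without touching the point.

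**2. When do the rules give different answers?** Only when the model still admits the dose after 2/2 DLTs. The criterion is: "Per EWOC, it should be unlikely (< 25% posterior probability) that the DLT rate at the dose will exceed 0.333". The plan states no figure to reproduce here, and Section 12.3.3.2 describes the prior as vague without values. The model results below therefore rest on assumed inputs.

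- Model: logit(π) = log(α) + β·log(d/d*), without covariates, evaluated on a grid; independent normal priors on log(α) and log(β), median β = 1.
- Four assumed wide priors: median DLT rate at d* of 0.10, 0.25 and 0.333 with SDs 2 and 1, and 0.25 with SDs 1.5 and 0.75.
- Assumed d* of 720 and 2000 mg. This gives 4 × 2 = 8 runs per dose and 24 over three doses.
- Assumed history: 0/3 at each lower level among 120, 240, 480 and 720 mg.
- Candidate doses: 120, 240, 360, 480, 600, 720, 900, 1080 and 1620 mg.
- A dose is admitted if P(π ≥ 0.333) < 0.25.

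*New top level, 2/2 DLTs:*

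| Dose | P(π ≥ 0.333) | Admitted |
|---|---|---|
| 480 mg | 0.31–0.66 | 0 of 8 |
| 720 mg | 0.25–0.73 (lowest run just under 0.25) | 1 of 8 |
| 1080 mg | 0.28–0.82 | 0 of 8 |

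The dose is blocked in 23 of 24 runs, so the rules agree.

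*Untested intermediate level (360, 600 or 900 mg), 2/2 DLTs, by the result at the next higher tested level (480, 720 or 1080 mg):*

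| DLTs at higher level | P(π ≥ 0.333) at intermediate level | Admitted |
|---|---|---|
| 0/3 | 0.05–0.17 | 24 of 24 |
| 1/6 | 0.06–0.16 | 24 of 24 |
| 1/3 | 0.18–0.45 | 7 of 24 |
| 2/6 | 0.18–0.37 | 7 of 24 |
| 2/3 | 0.41–0.77 | 0 of 24 |
| 2/2 | 0.51–0.93 | 0 of 24 |

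In the 1/6 case the model recommends the same dose in 10 runs and a higher one in 14. Such cohorts can arise, because 8.1.2.1.2 says that "additional cohorts of subjects may be enrolled at preceding dose levels, or to intermediate dose levels before or while proceeding with further dose escalation". If the intermediate level was opened because 2/2 or 2/3 subjects had DLTs above it, the rules agree in every run.

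The new-top-level result depends on the prior being wide. With 0/3 at 120, 240 and 480 mg, 2/2 at 720 mg and d* = 720 mg, a more informative prior (median 5%, SDs 1 and 0.5) gives P(π ≥ 0.333) = 0.07 at 720 mg and 0.23 at 1080 mg, so both would be admitted.

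**3. How often?** The probability of 2/2 DLTs at true rate p is p²: 0.166² = 0.028, 0.25² = 0.063, 0.333² = 0.111. The joint probability with at most 1/6 at the higher level (true rate q) is p² × [(1−q)⁶ + 6q(1−q)⁵]:

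- p = 0.05, q = 0.10: 0.0025 × 0.886 = 0.002
- p = 0.10, q = 0.15: 0.0100 × 0.776 = 0.008
- p = 0.166, q = 0.20: 0.0276 × 0.655 = 0.018
- p = 0.25, q = 0.30: 0.0625 × 0.420 = 0.026
- p = 0.333, q = 0.333: 0.1109 × 0.352 = 0.039

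These rates are assumed, and the results are conditional on such an intermediate cohort being opened. The documents do not say how often that would happen.

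**The case against.** The two texts can be reconciled. Exception 2 modifies the routine timing of dose decisions, and its content is mostly procedural: suspend, update, discuss, document. Its same-or-higher wording is conditional, so it can be read as an added hurdle where such a dose is otherwise open, not as lifting the bar at untested levels. The shorter restatements of exception 2 fit that reading. It is a fair construction, but the trigger's plain reference to any cohort does not compel it.

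Safeguards also apply on either reading. Enrollment is suspended, the recommended dose must meet EWOC, and "The parties must reach a consensus on whether to declare MTD, escalate the dose any further". This stands and is why the point is minor. But Section 12.3.3.3 treats the model's dose as guidance, and consensus governs how a choice is made, not which doses may be chosen.

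The run counts reflect assumed priors and histories and are not probabilities. That is correct: they show that the conflict can arise and where.

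Finally, where the rules consistently diverge, a higher dose has been tolerated, so forcing a lower dose could under-dose the next cohort. That cost is real, but it is the price the two-DLT rule already accepts at untested levels.

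**Conclusion.** The concern holds as a minor point. Two rules cover the same event at an untested dose level, they differ on whether that dose may be repeated or exceeded, and nothing states which prevails. That conclusion rests on the text alone.

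Its practical size rests on the assumed priors, reference doses and histories. With wide priors the conflict is close to absent at a new top dose. It is consistent only at an untested intermediate level below a higher dose with 0/3 or 1/6 DLTs. In the 1/6 case the joint probability is 0.002 to 0.039 over the assumed true rates, given that such a cohort is opened.

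**What to change.** In Section 8.1.2.1.2, limit the same-or-higher permission in exception 2 to previously tested dose levels. State that the two-DLT rule governs untested levels, and define intermediate as below the dose at which the two DLTs occurred. Align the synopsis (dose-escalation guidelines and Bayesian Adaptive Model) and Section 12.3.3.2 with that wording. If escalation has already ended, which the documents do not state, record in the study report which rule was applied if the situation arose.

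The change adds no patients or procedures. The sponsor and Investigators lose the discretion to repeat or exceed an untested dose after 2/2 DLTs when the model admits it. In the 1/6 case this overrides evidence from six subjects at a higher dose.
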